6.2.1.3 Electrocardiogram

Twelve-lead ECGs will be performed at study visits as described in the [Study Schedule of Activities](#). Pericarditis commonly involves changes in the electrophysiologic activity of the heart, resulting in typical ECG findings, namely widespread ST-segment elevation or PR-segment depression.

6.2.1.4 Echocardiogram

Echocardiographic assessment of presence of pericardial effusion including new or worsening of pericardial effusion should be obtained at study visits as described in the [Study Schedule of Activities](#). Pericardial effusion is characterized by accumulation of excess fluid in the pericardial space surrounding the heart, and pericarditis is one of the main causes of pericardial effusion. Echocardiography is a sensitive tool and the most widely used imaging technique for the detection of pericardial effusion and/or thickening. Echocardiograms are to be acquired per the ECHO core imaging parameters. Upon local assessment and interpretation, the ECHO is then to be submitted to the designated central imaging laboratory.

6.2.1.5 Patient Global Impression of Pericarditis Severity

Patient Global Impression questionnaires have been developed for a variety of indications. The PGIPS is a single-item PRO measure that assesses the subject's impression of overall severity of pericarditis symptoms at the time the questionnaire is administered, using a 7-point rating scale ranging from absent (no recurrent pericarditis symptoms) to very severe (recurrent pericarditis symptoms cannot be ignored) (Guy 1976). The PGIPS can be completed in less than 30 seconds.

The subject will select the box that best describes the severity of pericarditis symptoms right now:

- Absent: no symptoms
- Minimal: can be easily ignored without effort
- Mild: can be ignored with effort
- Moderate: cannot be ignored but does not influence my daily activities
- Moderately severe: cannot be ignored and occasionally limits my daily activities

- Severe: cannot be ignored and often limits my concentration on daily activities
- Very severe: cannot be ignored and markedly limits my daily activities

The PGIPS will be collected as described in the [Study Schedule of Activities](#).

6.2.1.6 Physician Global Assessment of Pericarditis Activity

Physician Global Assessment questionnaires have been developed for a variety of indications. The PGA-PA is a single-item clinician-reported outcome measure that investigators use to rate their impression of the patient's overall pericarditis disease activity at the time the assessment is completed, using a 7-point rating scale ranging from absent to very severe (Guy 1976). Like the PGIPS, the PGA-PA can be completed in less than 30 seconds.

The investigator will select the box that best describes subject's pericarditis activity right now.

- Absent
- Minimal
- Mild
- Moderate
- Moderately severe
- Severe
- Very severe

The PGA-PA will be collected as described in the [Study Schedule of Activities](#).

6.2.1.7 36-Item Short Form Health Survey

The SF-36 is a set of generic, coherent, and easily administered quality-of-life measures. The SF-36 was developed at RAND Corporation as part of its Medical Outcomes Study. The SF-36 assesses 8 health domains: physical functioning, bodily pain, role limitations due to physical health problems, role limitations due to personal or emotional problems, general mental health, social functioning, energy/fatigue, and general health perceptions. It also includes a single item that provides an indication of perceived change in health.

SF-36 will be collected in subjects ≥ 18 years or older as described in the [Study Schedule of Activities](#).

6.2.1.8 EQ-5D-5L

The EQ-5D-5L is a standardized instrument developed by the EuroQol Group as a measure of health-related quality of life that can be used in a wide range of health conditions and treatments. The EQ-5D-5L consists of a descriptive system and the EQ VAS. The descriptive system comprises 5 dimensions: mobility, self-care, usual activities, pain/discomfort and anxiety/depression. The rating scale records the subject's self-rated health on a vertical VAS. This can be used as a quantitative

measure of health outcome that reflects the subject's own judgement. The scores on these 5 dimensions can be presented as a health profile or can be converted to a single summary index number (utility) reflecting preferability compared to other health profiles (<https://euroqol.org/eq-5d-instruments>).

The EQ-5D-5L will be collected in subjects ≥ 18 years or older as described in [Study Schedule of Activities](#).

6.2.1.9 Insomnia Severity Index

The ISI is a 7-item self-report questionnaire assessing the nature, severity, and impact of insomnia. The usual recall period is the "last 2 weeks" and the dimensions evaluated are severity of sleep onset, sleep maintenance, early morning awakening problems, sleep dissatisfaction, interference of sleep difficulties with daytime functioning, noticeability of sleep problems by others, and distress caused by the sleep difficulties. A 5-point Likert scale is used to rate each item (e.g., 0=no problem; 4=very severe problem), yielding a total score ranging from 0 to 28. The total score is interpreted as follows: no clinically significant insomnia (0–7); subthreshold insomnia (8–14); clinical (moderate) insomnia (15–21); and clinical (severe) insomnia (22–28) (Morin et al 2011).

The ISI will be collected in subjects ≥ 18 years or older as described in [Study Schedule of Activities](#).

6.2.1.10 Cardiac MRI

Cardiac MRI will be performed as described in the [Study Schedule of Activities](#) at selected sites in approximately 10 subjects in the cardiac MRI substudy. Cardiac MRI will be performed to assess any changes in pericardial inflammation. Cardiac MRI readings will be performed by a central imaging laboratory. The study site/clinic reading of the MRI at the time of the examination may be used by the investigator for clinical decision-making.

6.2.2 Assessment of Clinical Response at the End of the Run-In Period Week 12/RW Baseline

At RI Week 12/RW baseline visit, all subjects receiving rilonacept who are able to discontinue background SOC pericarditis therapy during the RI period ([Section 3.1](#)) are assessed for Clinical Response. Only subjects who achieve Clinical Response at RI Week 12 and have discontinued background medications for pericarditis are eligible for randomization in the RW period.

Clinical Response at RI Week 12 is defined as follows:

- A weekly average of daily pericarditis pain of ≤ 2.0 on the 11-point NRS during the 7 days prior to and including the day of randomization, **AND**
- CRP level ≤ 0.5 mg/dL at the RI Week 12/RW baseline visit.

6.2.3 Management of Suspected Pericarditis Recurrence in the RW Period

Pericarditis Recurrence Definition: Pericarditis recurrence, for the purpose of the protocol, is defined as the recurrence of typical pericarditis pain associated with supportive objective evidence of pericarditis.

At any time point during the RW period, subjects who experience suspected recurrence of their pericarditis will have been instructed to inform their site investigator as soon as possible. Subjects who experience a suspected recurrence of pericarditis symptoms will be requested to report to the study site/clinic for a scheduled or unscheduled visit, during which clinical assessments will be performed to gather all the necessary diagnostic data to confirm or rule out the presence of pericarditis recurrence (Section 6.1.6.1). The investigator will evaluate all assessments performed for a diagnostic workup, whether at the study site or at locations outside.

Upon completion of pericarditis workup, the investigator is required to contact the [REDACTED] medical monitor to confirm that the protocol required diagnostic workup is complete prior to implementing treatment for the event.

Following communication with the [REDACTED] medical monitor, if the event meets the criteria for bailout rilonacept (at least 1 day with pericarditis pain measurement ≥ 4 on the 11-point NRS and one CRP value ≥ 1 mg/dL either on the same day or separated by no more than 7 days), and after the [REDACTED] medical monitor has confirmed with the investigator that the diagnostic workup is complete, the attainment of bailout criteria is confirmed in the IWRS, blinded study drug is discontinued, and open-label rilonacept treatment is dispensed. If needed, sequential ORT is allowed as outlined in Section 5.8.3. The subject will continue to be followed up according to the Study Schedule of Activities for the RW period.

[figure not shown]
Following communication with the [REDACTED] medical monitor, if the event does not meet the protocol criteria for bailout rilonacept but in the judgement of investigator requires treatment, after the [REDACTED] medical monitor has confirmed with the investigator that the diagnostic workup is complete, the investigator is allowed to add sequential ORT to blinded study drug, and as outlined in Section 5.8.3. Blinded study drug treatment will continue until a pericarditis recurrence that meets criteria for bailout rilonacept, or until the end of the RW period.

For a summary of management of suspected pericarditis recurrence, refer to Figure 3.

Upon suspected pericarditis recurrence, the event is required to be captured in the electronic data capture (EDC) system within 24 hours of learning of the event, and a pericarditis recurrence event adjudication package must be prepared for adjudication by CEC. The event package will include, but may not be limited to, data on the subject's pericarditis pain level, CRP value, ECG tracing, ECHO result, the presence or absence of pericardial rub, and any additional source documentation relevant to

the assessment of the suspected event. Details on endpoint package requirements will be described in the CEC charter. The CEC-confirmed pericarditis recurrences will be used for Primary Endpoint efficacy analysis. For more details on the CEC, refer to [Section 6.7.2](#)

Figure 3: Management of Suspected Pericarditis Recurrence in the Randomized-Withdrawal Period

6.3 Safety Assessments

Safety assessments to be performed at study visits are summarized in [Study Schedule of Activities](#) and include: assessment of AEs ([Section 6.4](#)), physical examinations (full and abbreviated) including vital signs measurements, chest x-ray, TB screening, and clinical laboratory tests (serology, hematology, chemistry, urinalysis) ([Section 6.6](#)). A pregnancy test ([Section 6.6.6](#)) will be conducted at screening and as needed during the study and must be performed 6 weeks after the last study drug administration.

6.3.1 Physical Examination

A full physical examination should include at minimum an evaluation of vital signs, head, eyes, ears, nose, and throat as well as cardiovascular, dermatological, musculoskeletal, respiratory, GI, genitourinary, and neurological systems. Body weight and height will be measured as per the [Study Schedule of Activities](#) and will be recorded in the eCRF. Any abnormality identified at baseline should be recorded on the medical history and physical examination eCRFs. At selected visits as specified in the [Study Schedule of Activities](#), an abbreviated physical examination will be performed to evaluate vital signs, lung and heart sounds, including evaluation for pericardial rub.

At all visits at the study site, limited symptom-directed physical examinations may need to be performed in order to determine changes from baseline or abnormalities and should be recorded in the subject's trial notes. New or worsened abnormalities should be recorded as AEs on the Adverse Event eCRF.

6.3.2 Vital Signs

Vital signs include measurements of respiratory rate, pulse rate, systolic and diastolic blood pressure, and temperature. Blood pressure measurements should be obtained after the subject has been seated for at least 5 minutes.

6.3.3 Chest X-ray

Chest x-rays in accordance with local requirements will be obtained at screening (or an existing chest x-ray within 12 weeks of first study drug administration can be used) according to the [Study Schedule of Activities](#). Chest x-rays should be reviewed by a qualified radiologist for clinically significant abnormalities and evidence of pulmonary disease that would exclude the potential subject.

6.3.4 Tuberculosis Screening

An IGRA test or another TB test based on acceptable clinical practice in each country will be performed in order to evaluate for the presence of active or latent TB infection at screening.

6.4 Adverse Events

The investigator is responsible for reporting all AEs that are observed or reported during the study, regardless of their relationship to study drug or their clinical significance.

6.4.1 Definitions

6.4.1.1 Adverse Event

An AE is any untoward medical occurrence in a subject or clinical investigation subject administered a pharmaceutical product. An AE does not necessarily have a causal relationship with this treatment.

An AE can therefore be any unfavorable sign (including an abnormal laboratory finding), symptom or disease temporally associated with the use of a medicinal (investigational) product, whether or not related to the medicinal (investigational) product. AEs also include: any worsening (i.e., any clinically significant change in frequency and/or intensity) of a pre-existing condition that is temporally associated with the use of the study drug; abnormal laboratory findings considered by the reporting investigator to be clinically significant; and any untoward medical occurrence.

6.4.1.2 Treatment-emergent Adverse Event

A treatment-emergent AE (TEAE) is defined as any event not present before exposure to the study drug or any event already present that worsens in either intensity or frequency after exposure to the study drug.

6.4.1.3 Serious Adverse Event

A serious adverse event (SAE) is any untoward medical occurrence or effect that, at any dose:

- Results in *death*. Includes all deaths, even those that appear to be completely unrelated to the study drug (e.g., car accident where the subject is a passenger).
- Is *life-threatening*. In the view of the investigator, the subject was at immediate risk of death from the event at the time of the event (i.e., it does not include an AE that might have caused death if it had occurred in a more serious form).
- Requires *in-patient hospitalization* or prolongs an existing hospitalization. (Complications occurring during hospitalization are AEs and are SAEs if they cause prolongation of the current hospitalization. Hospitalization for elective treatment of a pre-existing non-worsening condition is not, however, considered an AE. The details of such pre-existing condition must be recorded on the medical history or physical examination page of the eCRF. Hospitalization is defined as an admission to the hospital ward, a short-stay type unit, or Emergency Room for longer than 24 hours. Prolongation of existing hospitalization is defined as a hospital stay longer than originally anticipated for the event or development of a new AE as determined by the Investigator or treating physician.)
- Results in *persistent or significant disability/incapacity*. (An AE is incapacitating or disabling if it results in a substantial and/or permanent disruption of the subject's ability to carry out normal life functions.)
- Is a congenital anomaly/birth defect.
- Is an *important medical event*. Important medical events may not be immediately life-threatening or result in death or hospitalization but may jeopardize the subject or may require intervention to prevent one of the other serious outcomes listed above (e.g., intensive treatment in an emergency room or at home for allergic bronchospasm; blood dyscrasias or convulsions that do not result in hospitalization; or development of drug dependency or drug abuse).

In addition, medical and scientific judgment is required to decide if prompt notification is required in situations other than those defined for SAEs above, i.e., any event that the investigator regards as serious that did not strictly meet the criteria above but may have jeopardized the subject or required intervention to prevent one of the outcomes listed above, or that would suggest any significant hazard, contraindication, side effect, or precaution that may be associated with the use of the study drug.

All SAEs that occur after signing of study-related informed consent, whether or not the SAEs are related to the study drug or study procedures, must be reported.

6.4.1.4 Adverse Event of Special Interest

An adverse event of special interest (AESI) is defined as an AE of scientific and medical interest specific to the understanding of the study drug and requiring close monitoring and rapid communication by the investigator to the Sponsor. An AESI may be serious or non-serious. The rapid reporting of AESIs allows ongoing analysis of these events in order to characterize and understand them in association with the use of the study drug.

Treatments with immunosuppressants, including rilonacept, may result in an increase in the risk of malignancies. Therefore, malignancy is an AESI for rilonacept. Any AE of malignancy (excluding basal cell carcinoma of the skin) requires reporting to the [REDACTED] Pharmacovigilance (PHV) within 24 hours after the time the site personnel first learn about the event, following the process as described in [Section 6.4.6](#).

6.4.1.5 Adverse Reaction

Any noxious and unintended response to the study drug (i.e., where a causal relationship between the study drug and an AE is at least a reasonable possibility) related to any dose should be considered adverse drug reaction.

6.4.1.6 Suspected Unexpected Serious Adverse Reaction

Suspected Unexpected Serious Adverse Reaction (SUSAR) is an adverse reaction that is “unexpected”, i.e., it is not listed (or not listed at the severity that has been observed) in the designated Reference Safety Information of the Investigator’s Brochure. Evaluation and reporting requirements for SUSARs are detailed in [Section 6.4.8](#).

6.4.2 Assessing Adverse Events

6.4.2.1 Relationship to Study Drug

The investigator’s assessment of an AE’s relationship to the study drug is part of the documentation process, but it is not a factor in determining what is or is not reported in the study. If there is any doubt as to whether a clinical observation is an AE, the event should be reported.

The relationship or association of the study drug in causing or contributing to the AE will be characterized by investigator using the following classification and criteria:

- **Not Related:** when the AE is definitely caused by the subject's clinical state or the study procedure/conditions
- **Unlikely Related:** when the temporal association between the AE and the study drug is such that the drug is not likely to have any reasonable association with the AE
- **Possibly Related:** when the AE follows a reasonable temporal sequence from the time of study drug administration but could have been produced by the subject's clinical state or the study procedures/conditions
- **Related:** when the AE follows a reasonable temporal sequence from administration of the study drug, abates upon discontinuation of the drug, follows a known or hypothesized cause-effect relationship, and (if appropriate) reappears when the drug is reintroduced

6.4.2.2 Intensity

The severity of an AE will be recorded as one of the following:

- **Mild:** easily tolerated, does not interfere with normal daily activities, does not require intervention
- **Moderate:** causes some interference with daily activities; minimal, local, or noninvasive intervention indicated
- **Severe:** as a consequence of the event, daily activities are limited or completely halted; hospitalization or prolongation of hospitalization indicated

Changes in the severity of an AE should be documented to allow an assessment of the duration of the event at each level of intensity to be performed. Adverse events characterized as intermittent do not require documentation of onset and duration of each episode.

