1.3.1 Safety of Rilonacept

For a detailed review of the available rilonacept safety data, please refer to the current Investigator Brochure and the ARCALYST® package insert (Section 13.1: ARCALYST® Prescribing Information). The available rilonacept safety data is summarized below.

Rilonacept has been evaluated in 23 studies, including 22 complete and 1 ongoing. In the completed studies, 2243 subjects (2152 patients and 91 healthy volunteers) were exposed to rilonacept. Thirty of these patients were pediatric (<18 years of age).

Doses up to 320 mg subcutaneously (SC) once weekly and 2000 mg intravenously (IV) monthly have been studied for different indications, including CAPS, gout, and other inflammatory disorders.

Injection Site Reactions

In clinical studies with rilonacept, the most common and consistently reported AE associated with rilonacept was injection site reaction (ISR). The ISRs included erythema, swelling, pruritus, mass, bruising, inflammation, pain, edema, dermatitis, discomfort, urticaria, vesicles, warmth, and hemorrhage. Most ISRs were mild to moderate. In the gout clinical studies, approximately 1% of subjects treated with rilonacept discontinued due to ISRs. Similar results have been seen in other patient populations.

Infections

Interleukin-1 blockade may interfere with immune response to infections. Serious life-threatening infections have been reported in clinical trials in subjects treated with rilonacept.

Changes in Laboratory Parameters

Cholesterol and lipid levels may be reduced in patients with chronic inflammation. Subjects treated with rilonacept in clinical trials experienced increases in their mean total cholesterol, high-density lipoprotein (HDL) cholesterol, low-density lipoprotein (LDL) cholesterol, and triglycerides.

Immunogenicity

As with all therapeutic proteins, there is a potential for immunogenicity. Antibodies directed against the receptor domains of rilonacept were detected using an enzyme-linked immunosorbent assay (ELISA). In clinical trials with rilonacept, approximately 30% to 35% of subjects tested positive for treatment-emergent antibodies to rilonacept on at least 1 occasion.

Systemic Hypersensitivity Reactions

Hypersensitivity reactions are a potential risk with protein therapeutics in general. In clinical studies with rilonacept, systemic hypersensitivity reactions have been rare.

Malignancies

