6.4.3 Recording Adverse Events

Each subject should be monitored for the development of any AEs. This information should be collected by asking nonleading questions (such as "How are you feeling?") and from observations of and conversations with patients. AEs may also be collected by direct physical exam, diagnostic procedures, or any other appropriate source.

At every study visit (telephone or at the site), subjects will be asked a standard nonleading question to elicit any medically related changes in their well-being. They will also be asked if they have been admitted to the hospital, had any accidents, used any new medications, or changed concomitant medication regimens (both prescription and over-the-counter medications).

All AEs (serious and non-serious) will be documented in the subject's source documents and recorded in the eCRF. Any clinically relevant (as determined by the investigator) deterioration in laboratory assessments or other clinical findings is considered an AE and must be recorded in the subject's source documents and in the eCRF.

The AE term should be reported in standard medical terminology when possible. Also, when possible, signs and symptoms indicating a common underlying pathology should be noted as one comprehensive event. Information to be collected includes the following:

- Event term
- Date and time of onset
- Investigator-specified assessment of severity and relationship study drug
- Date of resolution of the event
- Seriousness
- Any required treatment or actions
- Outcome
- Whether or not it caused the subject to discontinue the study drug.
- Whether or not the AE is an Injection Site Reaction (ISR). ISR is defined as any AE that occurs at the study drug injection site. If an ISR is observed, the subject may be treated at the discretion of the investigator.

Adverse events resulting from concurrent illnesses, reactions to concurrent illnesses, reactions to concurrent medications, or progression of disease states must also be reported. All AEs will be followed to adequate resolution. The Medical Dictionary for Regulatory Activities (MedDRA) will be used to code all AEs.

Any medical condition that is present at the time that the subject is screened but does not deteriorate should not be reported as an AE. However, if the condition deteriorates at any time during the study, it should be recorded as an AE.

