7.7.8 Safety Analyses

Treatment-emergent AEs (TEAEs), defined as AEs that start or increase in severity after the first dose of study drug and before 6 weeks after the last dose of study drug, will be coded to system organ class and preferred term using the most recent version of MedDRA. TEAEs will be analyzed for all subjects combined and by treatment group in the RW period. Further analyses by severity and relationship to study drug as well as analyses of serious TEAEs will be presented.

Descriptive statistics will be used to summarize safety endpoints by visit for all subjects combined in the RI period and by treatment group in the RW period. Two-sided 95% CIs will be presented where meaningful. Data summaries will be displayed for clinical laboratory analyses (including safety

laboratory measurements, ADAs, etc.), vital signs measurements, ECGs, and physical examination findings.

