17 PATIENT COUNSELING INFORMATION

See FDA-approved patient labeling.

The first injection of ARCALYST should be performed under the supervision of a qualified healthcare professional. If a patient or caregiver is to administer ARCALYST, he/she should be instructed on aseptic reconstitution of the lyophilized product and injection technique. The ability to inject subcutaneously should be assessed to ensure proper administration of ARCALYST, including rotation of injection sites. (See *Patient Information Leaflet for ARCALYST*[®]). ARCALYST should be reconstituted with preservative-free Sterile Water for Injection to be provided by the pharmacy. A puncture-resistant container for disposal of vials, needles and syringes should be used. Patients or caregivers should be instructed in proper vial, syringe, and needle disposal, and should be cautioned against reuse of these items.

Injection-site Reactions: Physicians should explain to patients that almost half of the patients in the clinical trials experienced a reaction at the injection site. Injection-site reactions may include pain, erythema, swelling, pruritus, bruising, mass, inflammation, dermatitis, edema, urticaria, vesicles, warmth, and hemorrhage. Patients should be cautioned to avoid injecting into an area that is already swollen or red. Any persistent reaction should be brought to the attention of the prescribing physician.

Infections: Patients should be cautioned that ARCALYST has been associated with serious, life-threatening infections, and not to initiate treatment with ARCALYST if they have a chronic or active infection. Patients should be counseled to contact their healthcare professional immediately if they develop an infection after starting ARCALYST. Treatment with ARCALYST should be discontinued if a patient develops a serious infection. Patients should be counseled not to take any IL-1 blocking drug, including ARCALYST, if they are also taking a drug that blocks TNF such as etanercept, infliximab, or adalimumab. Use of ARCALYST with other IL-1 blocking agents, such as anakinra, is not recommended.

Vaccinations: Prior to initiation of therapy with ARCALYST physicians should review with adult and pediatric patients their vaccination history relative to current medical guidelines for vaccine use, including taking into account the potential of increased risk of infection during treatment with ARCALYST.

REGENERON

Manufactured and distributed by:

Regeneron Pharmaceuticals, Inc.

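### Section 6.4.2.2 lets an intermittent AE run undated across randomization, which puts the only controlled comparison of injection-site reactions at risk of attenuation

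*Protocol*

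**What the plan says.** The rule stands in Section 6.4.2.2 of both protocol versions (1.0 and 1.1): "Adverse events characterized as intermittent do not require documentation of onset and duration of each episode". The sentence before it reads: "Changes in the severity of an AE should be documented to allow an assessment of the duration of the event at each level of intensity".

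Section 6.4.3 lists what is collected for every recorded AE. The list includes "Date and time of onset", a resolution date, severity and an ISR flag, where "ISR is defined as any AE that occurs at the study drug injection site".

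Section 7.7.8 gives the analysis: "TEAEs will be analyzed for all subjects combined and by treatment group in the RW period". Treatment-emergent AEs are "defined as AEs that start or increase in severity after the first dose of study drug and before 6 weeks after the last dose". The first dose is the run-in loading dose. Section 6.4.1.2 defines the term more widely and also counts an existing event that becomes more frequent.

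Other provisions that bear on the point:
- Dosing is weekly (Section 5.2), and every subject receives rilonacept throughout the run-in (Section 5.9).
- Section 1.3.1 names ISR as the most common AE with rilonacept. The appended label (Section 13.1) tells physicians that "almost half of the patients in the clinical trials experienced a reaction at the injection site", and its Section 6.2 says that most reactions lasted one or two days.
- The run-in and the extension treatment period have no control arm (Section 7.3), so RW is the only controlled period.
- Safety is analyzed by the treatment actually received (Section 7.5).
- The randomization visit (Section 6.1.2.9) calls for an AE assessment but does not ask that open events be closed or re-dated.

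**The concern.** A reaction that lasts a day or two and returns after weekly injections can reasonably be called intermittent. A site that does so may enter one line with a run-in onset and add no dates for later episodes. If the reaction recurs after randomization at unchanged severity, the line shows neither a new start nor an increase in severity. If the recurrences stop because the subject now receives placebo, an open line does not show that either.

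The waiver also conflicts with Section 6.4.1.2. A rise in frequency makes an existing event treatment-emergent, yet frequency cannot be judged when episodes are not dated.

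What is at stake is the ISR comparison in RW, with about 25 subjects per arm (Section 7.4). A statistical analysis plan can choose how to assign events to periods, but it cannot recover dates that were never collected.

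**Working it through.** **Inputs.** The protocol has no design figure for ISR rates. The only controlled rates in it are in the appended label, Section 6.1, Table 1 (a six-week comparison in drug-naive CAPS patients):
- rilonacept 11/23 = 0.478 (48%)
- placebo 3/24 = 0.125 (13%)

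Both match the label's percentages. Using them as RW rates is an assumption. At 25 per arm they correspond to 25 × 0.478 = 12.0 and 25 × 0.125 = 3.1 subjects.

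**Counting by RW onset.** Let *q* be the share of RW reactors whose reaction is carried on a line with run-in onset. The documents give no value, so the full range is shown.
- Rilonacept recorded = 0.478 × (1 − *q*)
- Placebo recorded = between 0.125 × (1 − *q*), if the same share is masked there, and 0.125, if none is

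| *q* | Rilonacept | Placebo | Difference (points) |
|---|---|---|---|
| 0 | 48% | 13% | 35 |
| 0.25 | 36% | 9-13% | 23 to 27 |
| 0.5 | 24% | 6-13% | 11 to 18 |
| 0.75 | 12% | 3-13% | about 0 to 9 |
| 1 | 0% | 0-13% | −13 to 0 |

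The difference shrinks as *q* rises. With heavy masking in the rilonacept arm only, its sign can reverse.

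**Counting by overlap of onset and resolution with RW.** Rilonacept keeps its 48%. Placebo depends on how run-in lines are ended:
- ended at or before randomization: 13%
- left open: up to 1 − (1 − 0.125) × (1 − 0.478) = 0.543, or 54%, assuming that run-in and RW reactions are independent

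An open run-in line therefore hides the contrast by the other route.

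**Switch to open-label rilonacept.** A placebo subject who meets the bailout criteria has three treatment phases: run-in rilonacept, placebo, then open-label rilonacept. Section 7.4 assumes exponential times with a placebo median of 8 weeks, so expected recurrence by Week 24 is 1 − 0.5^(24/8) = 0.875. Not every recurrence meets the bailout criteria, but many subjects could have all three phases. One undated line across them cannot be assigned to the treatment received, as Section 7.5 requires.

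**The case against.** The other side has substance. The waiver is permissive and covers only events that the investigator calls intermittent; nothing says that ISRs are to be so called. A reaction that resolves before the next injection can equally be recorded as a separate AE. Event-level onset and resolution dates and the ISR flag remain, and a worsening after randomization is captured because severity changes must be documented. AEs are also assessed at every RW visit.

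A reader might infer that reactions begun in run-in cannot be counted in RW at all, and that the RW comparison is therefore biased towards no difference. The protocol does not support that. No section requires an RW onset for an event to count in RW, and overlap counting gives the right subject-level rates during blinded treatment if run-in lines are ended correctly. The rule for assigning events to periods is commonly left to the statistical analysis plan, which is not at hand, so its absence is no fault here.

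The consequence is also limited. RW safety is descriptive, and ISR is already a well-described, mostly mild to moderate effect.

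All of this stands. It makes the point conditional but does not remove it: the protection depends on site recording practice, and the protocol gives no instruction for a line that spans randomization or a treatment switch.

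**Conclusion.** The waiver puts the RW comparison of ISRs at risk of attenuation; it does not establish that the comparison is biased. The risk arises if sites carry repeated reactions on one line with a run-in onset. In that case neither simple counting rule fully repairs the record. Onset counting loses continuing reactors, mainly on rilonacept, and overlap counting can give placebo the run-in reactions.

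The size depends on the unknown share carried over, and ranges from no loss to complete masking. The illustration rests on CAPS rates in drug-naive patients being applied to subjects already treated for 12 weeks, and it shows direction and scale only. The same reasoning applies to any other intermittent AE that begins in run-in. This is a cheap improvement; it does not affect the efficacy conclusions.

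**What to change.** Amend Section 6.4.2.2 and the eCRF guidance. For ISRs and other intermittent AEs, the first episode after randomization, and the first after any switch to open-label rilonacept, is entered as a new AE record with its own onset date. The earlier record is ended at its last actual episode, so no administrative date stands in for a resolution date. Within a period the single-line convention can stay.

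The cost is one or two extra AE lines per affected subject and somewhat higher AE counts, because one recurring event is split at the period boundary. No dose, visit, endpoint or clinical management changes.
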